8.2 Randomisation Procedures

Allocation to trial groups

A total of 60 people will be recruited (56,57), which will allow calculation of 95% Confidence Intervals (CI) in the acceptable ranges for continuation to the main trial with the minimum size needed to estimate acceptability being 56 expected value 75% (95% CI = 59-87%). Participant randomisation will be undertaken centrally by the coordinating trial team at UCL using a randomisation system provided by Sealed Envelope and signed off by a UCL Research Contract Manager. Following participant consent, and confirmation of eligibility (see section 8.1 for pre-treatment assessments), the randomisation procedure described below will be carried out. Sealed Envelope will provide access to randomisation. Remote randomisation to treatment will be conducted by an adaptive web

randomisation service (Sealed Envelope). There is a Master Services Agreement between UCL and Sealed Envelope in place which covers all the work completed by this service provider from UCL. When the agreement is made for this study the Chief Investigator will complete a trial registration form (to be completed with the details for the study) and signed off by a UCL Research Contract Manager. Participants who satisfy the criteria will be eligible. We will record details of participants who do meet the inclusion criteria but are not randomised to inform the future fully powered RCT, which will consist of demographic and clinical details, and reasons of not consenting to the trial.

Participants will be considered as enrolled into the trial following: consent, pre-treatment assessments (see section 8.1), confirmation of eligibility, completion of the randomisation process, allocation of the participant trial number and intervention by the central coordinating team at UCL.

8.3 Intervention procedures

The proposed intervention will aim to:

- (1) increase the use of effective coping strategies for people with early-stage dementia by:
 - (a) identifying pleasant activities and agreeing to a plan of which activities to implement
 - (b) setting goals about implementing these
 - (c) monitoring and reviewing activities (on a weekly basis)
 - (d) teaching specific simple skills coping with stress (51)
 - (e) discussing accessing help
- (c) make a plan for the future

The intervention will be an individual home-based manualised programme, comprised of a total of 8 sessions. Participants and carers can repeat a session or a part of a session when necessary, and each of the sessions will last approximately 45 minutes (with homework between the sessions). The intervention will be delivered by a psychology graduate who will be trained in the intervention by the team. The psychology graduate will be supervised monthly by one of the CIs who is a Clinical Psychologist ([name]).

Adherence to treatment protocol

We will develop a manual guiding therapists in delivering the intervention. This manual will describe the key components of the intervention and will also specify training elements. We will also test the feasibility of measures assessing treatment adherence, such as audiotaping some of the sessions, and competency assessment, by developing a checklist for use in the main trial. This checklist will assess whether behavioural activation was the overall modality applied and if other therapeutic models were prominent in the therapy (i.e. cognitive therapy).

8.4 Subsequent assessments and procedures

This section describes all proposed outcome measures and assessments at each home visit.

Proposed outcome measures

Feasibility outcome measures

- The acceptability of the intervention for people with dementia and their carers (number of those finding the intervention acceptable)
- Willingness of clinicians to recruit and people with dementia to be randomised (number of dyads recruited per month and any barriers or facilitators to recruitment)
- Number of eligible participants that consent to the study
- Follow-up rates and number completing each outcome measure proposed for the main trial
- Number of sessions attended
- Standard deviations of outcome measures to estimate the sample size in a fully powered RCT

The acceptability of the programme to people with dementia, willingness of clinicians to recruit participants and of participants to be randomised, will be collected for feasibility analysis. We will also collect data on recruitment, attrition and questionnaire completion rates and estimate 'numbers needed' to plan a fully powered RCT of clinical and cost-effectiveness. Feasibility data on acceptability, completion rates and attrition will be supplemented by qualitative data. During qualitative interviews information will be collected on which outcomes will be of value to people with dementia, data relevant to the trial process itself, the randomisation procedure, and the methods of data collection.

Proposed clinical outcome measures

These will be evaluated for suitability for the main trial. Depressive symptoms is proposed as the outcome for the future fully powered study. Carers will complete generic health and quality of life measures (EQ-5D, SF-12), and resource use questionnaires to examine feasibility of cost-effectiveness analysis. Questionnaires will be completed at baseline, 4 and 8-months after randomisation.

Primary outcomes

1. depressive symptoms - *Cornell Scale for Depression in Dementia (CSDD)* (58). The CSDD, is a 19-item interviewer administered measure, using information by interviewing the person with dementia and their carer. Symptoms are described to the carer as they appear on the scale. Where there is a discrepancy between the carer and the researcher's ratings the carer is re-interviewed before making a final judgment.

Secondary outcomes

1. self-rated and carer-rated dementia-specific quality of life for the person with dementia – *DEMQOL* (59). The DEMQOL measures quality of life, by covering five domains, including daily activities, health and well-being, cognitive functioning, social relationships and self-concept. The scale uses both self and carer-rated reports of quality of life administered to the person with dementia and carer.

2. neuropsychiatric symptoms - *Neuropsychiatric Inventory (NPI)* (60). The NPI assesses 10 behavioural disturbances occurring in people with dementia, using a screening strategy to minimise administration time by examining and scoring only those behavioural domains with positive responses to screening questions. Both frequency and severity of each behaviour are determined, with both validity and reliability for the measure established.

3. health services utilisation - *Client Service Receipt Inventory (CSRI)* (61). We will use the CSRI to collect feasibility data on the use of health and social care services provided by public or non-public

bodies, and information on carer's costs and participant's use of health and social care services in order to inform the full trial. We will also collect data on medications for mental health, carer's provision of unpaid care and employment status, and any out-of-pocket costs to both participant and carer.

4. carers' mental health - Hospital and Anxiety Depression Scale (*HADS*) (62). Depressive symptoms in carers will be measured using the Hospital Anxiety and Depression Scale (HADS), a self-completed measure, generating scores for both generalised anxiety and depressive symptoms, used widely to identify caseness for clinically significant depression and anxiety.

5. carers' quality of life - EuroQoL EQ-5D (*EQ-5D*) (63) and Short Form-12 Health Survey (*SF-12*) (64). Carer health-related quality of life, will be measured using the three-level response version of the European Quality of Life-5 Dimensions (EQ-5D™). The EQ-5D is a standardised instrument for use as a measure of health outcome, applicable to a wide range of health conditions, providing a simple descriptive profile and a single index value for health status. Carers' mental and physical health, will be measured by the Short Form questionnaire-12 items (SF-12). The SF-12 measures health by scoring standardised responses, which are expressed in terms of two meta-scores: the physical component summary (PCS) and the mental component summary (MCS). A schedule of all trial assessments and procedures is set-out in Appendix.

8.5 Samples

8.5.1 Laboratory assessments

This section is Not Applicable to this project.

8.5.2 Translational research samples

This section is Not Applicable to this project.

8.5.3 Sample storage and transfer

This section is Not Applicable to this project.

8.6 Discontinuation/withdrawal of participants

In consenting to participate in the trial, participants are consenting to intervention, assessments, follow-up and data collection. A participant may be withdrawn from the trial whenever continued participation is no longer in the participant's best interests, but the reasons for doing so must be recorded (whenever possible). Reasons for discontinuing the trial may include:

- disease progression whilst on therapy
- intercurrent illness
- patients withdrawing consent

The decision to withdraw a participant from treatment will be recorded in the CRF and ISFs. If a participant explicitly states they do not wish to contribute further data to the trial their decision must be respected and recorded in the CRF.

8.7 Definition of End of Trial

The expected duration of the trial is 20 months from recruitment of the first participant (8 months on average for individual participants). The end of trial is the date of the last follow up home visit of the last participant.

9 Recording and reporting of adverse events

9.1 Unblinding

Protection against bias

In trials of psychological interventions, therapists and participants can not be blind to which intervention they are delivering or receiving. However assessors conducting assessments with participants, should not be aware of which treatment arm they belong to. All follow-up assessments after the intervention will be conducted by a researcher who is blind to treatment allocation. Given that participants may occasionally and inadvertently inform researchers of the treatment they are receiving, we will reduce this effect by providing explicit reminders to participants. We will record instances of loss of blinding to inform procedures for the main trial.

Emergency unblinding:

This section is Not Applicable to this project as it is a single-blinded trial. We will seek advice on issues of blinding by the UCL Research Service and Senior Trialists in the Division of Psychiatry.

9.2 Notification of reportable protocol violations

A reportable protocol violation is a breach which is likely to effect to a significant degree:

- (a) the safety or physical or mental integrity of the participants of the trial; or
- (b) the scientific value of the trial.

The sponsor will be notified immediately of any case where the above definition applies during the trial conduct phase. The CI or designated individual will notify the sponsor of any protocol violation.

9.3 Trust Incidents and Near Misses

An incident or near miss is any unintended or unexpected event that could have or did lead to harm, loss or damage that contains one or more of the following components:

- a. It is an accident or other incident which results in injury or ill health.
- b. It is contrary to specified or expected standard of patient care or service.
- c. It places patients, staff members, visitors, contractors or members of the public at unnecessary risk.
- d. It puts the Trust in an adverse position with potential loss of reputation.
- e. It puts Trust property or assets in an adverse position or at risk.

Incidents and near misses will be reported to the Trust through DATIX as soon as the individual becomes aware of them. A reportable incident is any unintended or unexpected event that could have or did lead to harm, loss or damage that contains one or more of the following components:

- a) It is an accident or other incident which results in injury or ill health.
- b) It is contrary to specified or expected standard of patient care or service.
- c) It places patients, staff members, visitors, contractors or members of the public at unnecessary risk.
- d) It puts the Trust in an adverse position with potential loss of reputation.
- e) It puts Trust property or assets in an adverse position or at risk of loss or damage.

10 Data management

10.1 Confidentiality

All data will be handled in accordance with the UK Data Protection Act 1998. The Case Report Forms (CRFs) will not bear the participant's name or other personal identifiable data. The participant's initials, date of birth and trial identification number, will be used for identification and this will be clearly explained to the patient in the Patient information sheet. Patient consent for this will be sought. All participant information will be stored in accordance with the UK Data protection Act 1998 guidance, with all personally identifiable information, stored in locked cabinets and stored separately from study data which will be anonymised and saved on password-protected computers at University College London. Each participant will be assigned an identification code, which will be used in all data storage, and will not contain any names or other personally identifiable information. After completion of the study all personal details will be deleted. **If any person in the study tells us that they or someone else is being harmed we will ask their permission to disclose the information to the Older People's Community Mental Health Team (or Memory Clinic) or other appropriate responsible person. We respect confidentiality but cannot keep it a secret if anyone is being harmed (See Participant Information Sheets).**

10.2 Data collection tools and source document identification

Data will be collected from sites on trial specific CRFs or data collection tools such as electronic CRFs. Source data contained in source documents will be accurately transcribed on to the CRFs. Methods to maximise completeness of data will be applied when necessary. The PI will have the primary responsibility of ensuring all data entered in the CRFs are accurate. A delegation log will identify all those personnel with responsibilities for data collection and handling, including those who have access to the trial database (PI, CIs, Trial statistician, Research Assistant).

10.3 Completing Case Report Forms

All CRFs will be completed and signed by staff that are listed on the site staff delegation log and authorised by the PI to perform this duty. The PI will be responsible for the accuracy of all data reported in the CRF. In line with UCL Data Protection Policy trial documentation and anonymous data will be securely kept for a period of 20 years following completion of the trial. All data of all sites taking part in this project will be kept and monitored at UCL. The PI and or a designated individual will be responsible for any data queries.

10.4 Data handling

In the study, data will be collected from patients in accordance with the patient consent form, patient information sheet and section 8.4 of this protocol. UCL, as the study sponsor will act as the data controller for the study. The PI, the study Statistician or a designated individual will process, store and dispose of the data in accordance with all applicable legal and regulatory requirements, including the Data Protection Act 1998 and any amendments thereto. All data will be stored centrally at a locked filing cabinet at UCL controlled by the PI. The data will not be transferred to any party not identified in this protocol and will not to be processed and/or transferred other than in accordance with the patients' consent.

Quality control

Compliance to GCP is now a requirement for all clinical trials. Accurate records will be kept, in line with the research protocol, in relation to recruitment, randomisation and data collection. We will collect and manage data in a systematic way, and researchers will be trained, supervised and supported. Compliance to GCP, and Quality Control (QC) will be monitored in the beginning monthly and every three months subsequently. The PI will ensure that all records are maintained and participant confidentiality is assured. We will perform a QC to a sample of data during the first weeks of data collection. Investigator Site Files (ISF) and a Master file will also be kept that will source all documents of the study.

11 Statistical Considerations

11.1 Primary Outcome

Feasibility primary outcome

- The acceptability of the intervention for people with dementia and their carers which will be measured by the number of those finding the intervention acceptable

11.2 Secondary outcome(s)

- Willingness of clinicians to recruit and people with dementia to be randomised (number of dyads recruited per month and any barriers or facilitators to recruitment)
- Number of eligible participants that consent to the study
- Follow-up rates and number completing each outcome measure proposed for the main trial
- Number of sessions attended
- Standard deviations of outcome measures to estimate the sample size in a fully powered RCT

Proposed clinical outcome measures

- These will be evaluated for suitability for the main trial. Depressive symptoms is proposed as the outcome for the future fully powered study. Carers will complete generic health and quality of life measures (EQ-5D, SF-12), and resource use questionnaires to examine feasibility of cost-effectiveness analysis. Questionnaires will be completed at baseline, 4 and 8-months after randomisation. For further details see Section 8.4.

11.3 Sample size calculation

Proposed sample size for feasibility trial

No formal power calculations are undertaken in feasibility studies, instead sufficient participants are recruited in order to determine factors such as attrition and recruitment rates and how these are related to feasibility for a full scale RCT. A total of 60 people will be recruited (56,57), which will allow calculation of 95% Confidence Intervals (CI) in the acceptable ranges for continuation to the main trial with the minimum size needed to estimate acceptability being 56 expected value 75% (95% CI = 59-87%). We will recruit to the study over 15 months, with an average of 4 dyads recruited per month.

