Generally we do not anticipate any risks to people with dementia through participation. The information sheets will provide participants with information about the possible benefits and known risks of taking part in the trial. Participants will be given the opportunity to discuss this with the researcher prior to consenting to the study. There appear to be no documented harmful side effects from taking part in behavioural activation interventions. The only potential risk we can identify associated with the proposed research is that people may find either the intervention or the assessments upsetting or distressing, for example highlighting pleasant activities that they can no longer do, or do so independently. However given previous preventive trials of behavioural activations in several populations, and the Cochrane review published by the PI on psychological interventions for people with dementia, this is expected to be infrequent. Most people find behavioural activation sessions enjoyable, and feel comfortable in taking part in these types of interventions. At any point where a participant or carer becomes uncomfortable with the assessments they will be discontinued. The researcher running the sessions and completing the assessments will be advised to discontinue the assessment/intervention sessions, and participants will be given further support and will be debriefed as necessary. For example, they will be encouraged to **Speak to one of the team members, and/or ring the Alzheimer's Society National Dementia Helpline (see Participant Information Sheets)**. Local lone working policies for all staff involved will apply in relation to assessment and management of risk for UCL staff.

4 Objectives

Primary: The primary objective of the study is to develop a coping intervention based on behavioural activation to prevent depressive symptoms arising or worsening and promote well-being in people with early-stage dementia.

Secondary: The secondary objective is to assess the feasibility and acceptability of the intervention via a feasibility RCT in order to inform a future fully powered RCT of clinical and cost-effectiveness.

5 Trial design

Study design: Feasibility RCT, of 2 treatment arms (Behavioural Activation vs treatment as usual) over 8 weeks, assessing the acceptability and feasibility of behavioural activation for preventing depressive symptoms in early-stage dementia (see Figure 1, in Appendix 1).

6 Selection of Participants

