6.3 Recruitment

Sample

The study will recruit 40 participants for consultations in the development of the intervention (focus groups and individual interviews, for further details see **Stage 2a: Work Package 2**), and a total of 60 people with dementia and their carers in the feasibility RCT. People with dementia will be recruited from Memory Clinics and Community Mental Health Teams (CMHTs). The control condition will be usual care, and use of drugs will be documented for both conditions. Recruitment will take place in two NHS Trusts, the Camden and Islington Foundation Trust (C&IFT), and the Barnet, Enfield and Haringey Mental Health Trust. We predict that a minimum of one dyad per week will be recruited into the study. This is based on previous experience from the REMCARE trial, during which the lead Applicant recruited an average of 8 people with dementia per month in London, and the recently completed iCST trial which recruited on average 9 people per month.

Recruitment Strategy

People with dementia living in the community and their carers will be recruited from a variety of settings including CMHTs, memory clinics, outpatient clinics, and day centres. Essential baseline

information will be recorded at registration, with people with dementia individually randomised using an adaptive scheme. People on cholinestarease inhibitors or antidepressant medication will continue taking them. The researcher and the PI will make close links with the local memory clinic and community mental health teams through regular attendance and contact.

Participant recruitment at a site will only commence when the trial has:

1. Been confirmed by the Sponsor (or it's delegated representative), and
2. Been issued an 'NHS permission letter'.

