8.1 Pre-intervention assessments

There are no specific pre-intervention assessments other than screening participants for inclusion criteria and the baseline assessments. People with dementia that meet the inclusion criteria and their carers will be recruited from several settings and existing networks (i.e. Community Mental Health Teams for Older People (CMHTs), Memory Clinics, Outpatient Clinics, Day centres). Baseline information required for eligibility will be recorded by memory clinics, day centres, and CMHTs. Participants will be recruited by engaging with professionals in the above settings and will be identified by the researcher using the networks above. We will use RCT methodology with remote randomisation, which will be provided by Sealed Envelope. There is a Master Services Agreement between UCL and Sealed Envelope in place. The PI will complete a trial registration form to be completed with all the details for the study and then signed off by a UCL Research Contract Manager, at University College London. See Section 8.4 for details of assessment procedures.

All pre-treatment procedures will be carried out as specified in the schedule of assessments (Appendix 4).

Treatment as usual

This study is designed to be a pragmatic trial, and no participants will be denied access to any treatment that they would have access to have they not taken part in the study. Both groups will also receive care as usual, details of which will be recorded for each participant. The treatment as usual control group (TAU) will not receive any additional intervention. We will assess the feasibility of collecting service use data, which will allow us to identify services received in both groups and any changes that occur.

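### The precision statement for acceptability does not hold: 59-87% is not the 95% interval for 75% of 56, and the denominator should be the Behavioural Activation arm, not the 60 randomised

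*Protocol*

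**What the plan says.** Section 11.3 disclaims a formal power calculation and justifies the total of 60 by precision, "which will allow calculation of 95% Confidence Intervals (CI) in the acceptable ranges for continuation to the main trial". It then gives the "minimum size needed to estimate acceptability being 56 expected value 75% (95% CI = 59-87"%. Section 8.2 carries the same statement.

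The outcome concerned is the primary feasibility outcome of section 11.1: "The acceptability of the intervention for people with dementia and their carers which will be measured by the number of those finding the intervention acceptable".

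Three other places fix who can supply that rating:

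- Section 6.3 sets the size as "a total of 60 people with dementia and their carers in the feasibility RCT".
- Section 5 describes a "Feasibility RCT, of 2 treatment arms (Behavioural Activation vs treatment as usual) over 8 weeks".
- Section 8.1 says: "The treatment as usual control group (TAU) will not receive any additional intervention".

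On allocation, section 6.3 says only "people with dementia individually randomised using an adaptive scheme". The readable text gives no allocation ratio, no arm size, no interval method and no allowance for dropout.

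**The concern.** A sample size, an expected proportion and a confidence interval are tied together by arithmetic. Given any two, the third follows up to the choice of method. Here the printed interval is 28 points wide, which is too wide for 56 observations at 75%.

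Separately, the text moves from 60 recruited to a minimum of 56 for acceptability, as if nearly everyone randomised could judge the intervention. Only those offered Behavioural Activation can do so.

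The protocol links this interval to the decision on continuing to the main trial. A reader weighing that decision would therefore rely on a precision figure that does not follow from its stated size, and on a size that the design does not supply for this outcome.

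**Working it through.** **Inputs.** Expected proportion p = 0.75, n = 56, interval 59-87% at 95% (sections 8.2 and 11.3). Total randomised 60 people with dementia, each with a carer (6.3). Two arms (5). Usual care gets no added intervention (8.1).

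**Step 1: try to reproduce the printed interval.** 75% of 56 is 42.

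- Wald: p ± 1.96·√(p(1−p)/n) = 0.75 ± 1.96·√(0.1875/56) = 0.75 ± 0.113, so 63.7-86.3%.
- Wilson: centre (p + z²/2n)/(1 + z²/n) = 0.7843/1.0686 = 0.734. Half-width z·√(p(1−p)/n + z²/4n²)/(1 + z²/n) = 0.1185/1.0686 = 0.111. Result 62.3-84.5%.
- Exact (Clopper-Pearson): lower limit is the 2.5% point of Beta(42, 15), upper limit the 97.5% point of Beta(43, 14). Result 61.6-85.6%.
- Continuity-corrected Wald gives 62.8-87.2%, continuity-corrected Wilson 61.4-85.2%, Agresti-Coull 62.2-84.6%, Jeffreys 62.6-84.9% and logit 62.1-84.6%.

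None gives 59-87%. Lower limits run from 61.4% to 63.7%, and widths are about 22 to 24 points against the printed 28. Using 99% does not explain it either: Wald 60.1-89.9%, exact 57.5-88.1%, Wilson 58.0-86.7%.

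**Step 2: find what does give 59-87%.** A search over n = 20 to 79 at 75% finds intervals rounding to 59-87% only for n of about 33 to 43, depending on method. The exact method gives it for n = 39 to 43. The whole-number case is 30/40, exact 58.8-87.3%.

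**Step 3: who can rate acceptability.** For 56 people with dementia (or 56 dyads) to rate the intervention, 56/60 = 93% would have to be allocated to Behavioural Activation, a ratio of 14:1. If both members of a dyad are counted, 28 dyads give 2 × 28 = 56 ratings, which 1:1 allocation would allow. Those ratings come in pairs. With within-dyad correlation ρ the effective number is 56/(1 + ρ), which lies between 56 (ρ = 0) and 28 (ρ = 1).

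**Step 4: the interval by arm size.** The ratio is not stated, so two cases are shown as assumptions. 75% of 30 is 22.5, so both neighbouring counts are given.

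| Assumed allocation | Behavioural Activation arm | Count | Exact 95% CI | Width (points) |
|---|---|---|---|---|
| 1:1 | 30 | 22/30 | 54.1-87.7% | 33.6 |
| 1:1 | 30 | 23/30 | 57.7-90.1% | 32.4 |
| 2:1 | 40 | 30/40 | 58.8-87.3% | 28.5 |

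For an outcome measured in both arms, 45/60 gives 62.1-85.3%. All rows assume that everyone in the denominator supplies a rating.

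**The case against.** The strongest defence is that the printed interval may be right and only the 56 misplaced. If 60 were randomised 2:1, the Behavioural Activation arm would be 40, and 59-87% is then the correct exact interval for those who receive the intervention. The documents do not exclude this. The flow diagram, where arm sizes might appear, is not reproduced in the available copy.

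A reader might therefore infer too much in three ways:

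- **That the arm is about 30, so the true interval is necessarily wider than stated.** This assumes 1:1 allocation, which no readable text gives.
- **That 56 can never be reached.** Section 11.1 includes carers, so 56 ratings are attainable from 28 dyads. They would not be 56 independent ratings, and even 56 independent ratings do not give 59-87%.
- **That 59-87% can only have come from 30/40.** Other denominators from about 33 to 43 also round to it, and the protocol names no method.

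An unstated allowance could also bridge 56 and 40: a within-dyad correlation of 0.4 (56/1.4 = 40), or ratings from 71% of 56 (40/56). The protocol mentions neither.

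It is also fair to say that the analyses are descriptive, that no numerical progression threshold is attached to the 59%, and that section 11.3 cites two pilot-size references besides this interval. These points limit the consequence. They do not make the three figures agree, and the statement is the protocol's own, not a detail left to the analysis plan.

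**Conclusion.** The point holds in two parts.

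First, 56, 75% and 59-87% are mutually inconsistent by every standard method, in both sections. At n = 56 the exact interval is 61.6-85.6%; the printed one fits a denominator of about 40. This needs no assumption.

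Second, the denominator for acceptability is the Behavioural Activation arm. A minimum of 56 people with dementia or dyads cannot come from 60 randomised in two arms unless about 93% are allocated to that arm.

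The effect on the stated precision depends on the allocation ratio. Under 1:1 the lower limit falls from 59% to about 54-58% and the width rises from 28 to about 32-34 points. Under 2:1 the printed interval stands and only the 56 is wrong. The documents do not settle which applies. The target of 60 is not called into question.

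**What to change.** Amend sections 8.2 and 11.3 together:

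1. Remove 56 as the minimum size for acceptability.
2. State the allocation ratio and the planned number in the Behavioural Activation arm, and base the precision statement on that number.
3. Count people with dementia and carers separately, so that paired ratings are not treated as independent.
4. Name the interval method and print the matching interval at an expected 75%. With the exact method this is about 54-88% (22/30) to 58-90% (23/30) if the arm is 30, or 59-87% (30/40) if it is 40. Do not replace 59-87% before the ratio is confirmed.
5. Use n = 60 precision (45/60: 62-85%) only for outcomes measured in both arms, such as follow-up and questionnaire completion.

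The cost is a few sentences. No further participants are needed, and the stated precision may become slightly less favourable.
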